6.12 Estimated Trial Calendar

Trial will begin enrollment in April 2018 and will continue until 1,386 subjects are enrolled. Last patient off study is expected to be accomplished by March 2020 and close-out activities and clinical trial report will follow within 7 months after.

7. STUDY PROCEDURES, ASSESSMENTS AND DATA COLLECTION

Embryos will be observed until they are transferred and then the clinical outcome of all subjects will be recorded until the ongoing pregnancy is verified (up to 10-12 weeks of gestation).

Subjects will be followed up until lost to follow-up, meeting the withdrawal or premature discontinuation criteria (as defined in Sections 6.9 and 10.13), or exiting from the trial (as defined in Section 6.10), whichever comes first.

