6.7 Randomization and Allocation of Subjects

After signing the informed consent form, all eligible subjects will be randomized and allocated to either of the two treatment groups immediately after fertilization check on Day 1 of embryo culture.

A stratified block randomization with fixed block length and allocation ratio 1:1 will be used. The stratification will be based on site and the age of subject (age group 18-35 vs. 36-40). Randomization will be accomplished using the Interactive Web Response Services (IWRS) system. An independent statistician will generate the

Protocol Version: 3.0 / Jan 31, 2018 21 / 49

Study Number: MS200497_0006

randomization schedule and upload to the IWRS system. All randomization codes will not be reused and subjects who discontinue the study early will not be replaced.

A subject can be considered as a drop-out during the study if she is randomized but primary endpoint data is not available for this subject, for whatever reason. Reasons for study discontinuation will be recorded in the Trial Exit eCRF.

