8. STATISTICS

8.1 Sample Size

Based on an expected clinical pregnancy rate of 30% (Adamson et al., 2016) in the control group and a 25% relative increase of clinical pregnancy rate in the experimental group, a two-sided test with an alpha level of 0.05 needs 623 subjects per group to reach a power of 80%. With a drop-out rate of 10%, 1,386 subjects (693 per group) need to be randomized. A subject can be considered as a drop-out during the study if she is randomized but primary endpoint data is not available for this subject, for whatever reason.

The calculation of sample sizes was performed using nQuery Advisor® version 7.0.

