10.13 Trial or Site Discontinuation

Protocol Version: 3.0 / Jan 31, 2018 46 / 49

trial

· At any time of the study, due to adverse events, or risks outweighing the benefit as determined by the investigators;

Merck KGaA may temporarily or permanently discontinue the trial at a single site or at all sites for ethical, compliance or other reasons. If this is necessary, Merck KGaA will endeavor to provide advance notification to the site. If the site or trial is suspended or discontinued, the Investigator will be responsible for ensuring prompt notification to the EC. Where required by local regulations, Merck KGaA will be responsible for informing the EC of trial or site discontinuation.

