#### 10 Trial Subjects

#### 10.1 Disposition of Subjects and Discontinuations

A table with

- Number of subjects screened
- Number of subjects with screen failure
- Number of subjects enrolled in the study
- Number of subjects randomized in the study
- Number of subjects in Full Analysis (FA) dataset
- Number of subjects in Per Protocol (PP) dataset
- Number of subjects completed the study as per protocol
- Subject completed the study as per protocol and appropriate outcome (Failed to conceive/ Biochemical pregnancy/ Spontaneous Miscarriage/ Clinical pregnancy/ Ongoing pregnancy/ Subject underwent therapeutic abortion/elective abortion)
- Number of subjects who discontinued from the study
- Subject did not complete the study as per protocol and appropriate outcome (Fresh embryo transfer was cancelled/ Subject requested to be withdrawn after embryo transfer/ Investigator withdrew subject/ Imaging was discontinued prior to completion/ Subject was lost to follow-up/ Subject was non-compliant/ Other)
- Fresh embryo transfer was cancelled, appropriate reason (No cleavage/ No viable embryo for transfer/ Freeze all due to elevated risk of OHSS/ Other)

will be summarized as number and percentage for both the treatment groups and overall.

Subjects Screened are the subjects for whom "Date informed consent signed by subject/partner" is available.

Subjects enrolled in the study are the subjects who satisfy both the inclusion and exclusion criteria.

Screen failure subjects are the subjects who are screened but not satisfying any one of the inclusion or exclusion or both criteria.

Listing will be provided for details of randomized subjects from (FA) dataset.

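### Protocol section 7 stops follow-up at discontinuation, so pregnancy outcomes that could still be obtained go missing and the SAP counts them as non-pregnancies

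*Protocol*

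**What the plan says.** Protocol section 7 contains two statements that pull apart. Its first paragraph says the clinical outcome of all subjects is recorded until ongoing pregnancy is verified at weeks 10-12. Its second paragraph ends follow-up earlier: "Subjects will be followed up until lost to follow-up, meeting the withdrawal or premature discontinuation criteria (as defined in Sections 6.9 and 10.13"), or at trial exit under section 6.10, whichever happens first.

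- **Section 6.9** deals with the woman's own right to withdraw. It keeps her data up to the point where consent is withdrawn.
- **Section 10.13** gives one ground as "At any time of the study, due to adverse events, or risks outweighing the benefit as determined by the investigators". It also lets the sponsor stop one site or all sites for ethical, compliance or other reasons. It does not say what happens to the outcomes of women already randomised. Section 10.14 starts close-out on termination, with no step for completing them.
- **Section 6.7** defines the result: "A subject can be considered as a drop-out during the study if she is randomized but primary endpoint data is not available", whatever the reason.
- **SAP 10.1** lists reasons for non-completion, among them "Subject requested to be withdrawn after embryo transfer/ Investigator withdrew subject", discontinued imaging, non-compliance, loss to follow-up and cancelled transfer.
- **Protocol 8.4.1 and SAP section 9** impute nothing. SAP 14.1 divides women with a fetal heartbeat by women with a transfer attempted.

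**The concern.** The allocated intervention is over on Day 3. What remains for the primary endpoint is an hCG test, which section 7.4 places under site routine, and a scan at weeks 6-8. Section 5.2.1 accepts clinical documentation as evidence of the endpoint. A woman withdrawn by the investigator, or whose site closes, may still have her result in the clinic's own records, but the plan has no route for collecting it.

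The clinicians and embryologists who can influence individual exits know the arm (section 6.6). If the SAP's discontinued-imaging category means time-lapse imaging, it can occur only in the GERI+ arm. Losses could therefore differ between arms. Each one lowers the reported pregnancy rate whenever the missing outcome was a pregnancy.

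**Working it through.** **Plan's own figure.** Inputs from Protocol 8.1: control rate 30%, "a 25% relative increase of clinical pregnancy rate in the experimental group" (so 37.5%, a difference of 7.5 points), two-sided alpha 0.05, power 80%. The mean rate is 0.3375.

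n per arm = [1.960 × √(2 × 0.3375 × 0.6625) + 0.842 × √(0.30 × 0.70 + 0.375 × 0.625)]² / 0.075² = 623.

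623 / 0.90 = 692.2, rounded up to 693; 2 × 693 = 1,386. The stated figures reproduce.

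**How a missing scan is counted.** SAP section 9 lets visit-based percentages use women still in the trial, but only where nothing else is specified. SAP 14.1 does specify: the denominator is transfers attempted. A transferred woman without a scan result is in the denominator and cannot be in the numerator. With true rate p and a fraction d of transferred women lost independently of outcome, the reported rate is p × (1 − d).

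**Equal losses (d assumed).** The difference becomes 7.5 × (1 − d) points.

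| Loss in each arm | Control | GERI+ | Difference (points) |
|---|---|---|---|
| 2% | 29.4% | 36.75% | 7.35 |
| 5% | 28.5% | 35.6% | 7.1 |
| 10% | 27.0% | 33.75% | 6.75 |

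**Unequal losses, no true effect (30% in both arms, losses assumed).** The spurious difference is 0.30 × the gap in loss.

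- 5% v 10%: 28.5% v 27.0%, which is 1.5 points, or 20% of the planned 7.5.
- 2% v 8%: 29.4% v 27.6%, which is 1.8 points.
- 0% v 10%: 30.0% v 27.0%, which is 3.0 points.

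For an unstratified two-sided 5% test with 693 per arm, the 5% v 10% case raises the rejection rate to about 9.6%. That bears on the CMH test in Protocol 8.4.2. SAP section 7 has since dropped between-group comparisons, so under the SAP the effect is on the reported rates.

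**A trial-level stop.** Planned accrual is 1,386 / 21 = 66 a month, and 66 × 12 / 52 = 15.2 a week. Randomisation is on Day 1 and transfer on Day 3. The hCG result at 12-18 days after transfer therefore comes about 2-3 weeks after randomisation. Gestational weeks 6-8 are about 4-6 weeks after it, since section 5.2.2 equates 20 gestational weeks with 18 weeks after fertilisation. Women with a negative hCG leave with a known outcome. Assuming 40% are positive:

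- lower: 15.2 × 2 + 15.2 × 2 × 0.4 = 43 women
- upper: 15.2 × 3 + 15.2 × 3 × 0.4 = 64 women

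With 30% to 50% positive, the range is 40 (15.2 × 2 × 1.3) to 68 (15.2 × 3 × 1.5). Cancelled transfers would lower all of these.

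**The case against.** **The rule's reach is narrow.** Section 6.9 covers only the woman's own withdrawal, which must be respected. Section 10.13 is headed as trial or site discontinuation. Its investigator bullet has no lead-in in the available text, so it is unclear whether it refers to a woman, a site or the trial. Investigator withdrawal appears as a reporting category in the SAP, not as a defined criterion. All this stands. It limits the avoidable loss to investigator withdrawal, non-compliance, stopped imaging and closure, and no document says how common these are.

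**The drop-out allowance is not the size of this problem.** Protocol 8.1 says: "With a drop-out rate of 10%, 1,386 subjects (693 per group) need to be randomized". A reader might infer that this rule loses about 70 women per arm (693 − 623) and takes 3.0 and 3.75 points off the two rates. The documents do not support that. The 10% covers every cause. Cancelled transfers fall outside the SAP denominator, and genuine loss to follow-up and withdrawn consent would not be recovered by any change here.

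**Closure is not arm-specific.** A reader might also infer that stopping a site or the trial biases the comparison. Allocation is 1:1 in blocks within site and age stratum, so closure removes the arms about equally and mainly costs precision. Only individual exits could bias the rates by arm.

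**The loss would be visible.** SAP section 9 shows missing counts as a category, and SAP 10.1 tabulates exit reasons by arm. That would reveal an imbalance but would not recover the outcomes.

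**The scan may not be routine.** Routine status is explicit only for hCG. For the week 6-8 scan it is inferred, chiefly from the endpoint's acceptance of clinical documentation. This stands as a caveat.

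**Conclusion.** The point holds as an avoidable source of missing primary outcomes. Section 7 contradicts its own opening promise, and nothing elsewhere restores outcome collection. SAP 14.1 then scores the missing outcomes as non-pregnancies among women with a transfer attempted.

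Its actual size is unknown. The 1.5-point spurious difference (5% v 10% lost, 30% in both arms) and the shrinkage from 7.5 to 7.35-6.75 points (2-10% lost equally) rest on assumed loss rates among transferred women and on loss unrelated to outcome.

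Two further readings go too far. One is that every woman within 4-6 weeks of randomisation (15.2 × 4 to 15.2 × 6, about 61-91) would be lost at a trial stop. Women with a negative hCG already have an outcome, so about 43-64 would be waiting if 40% test positive. The other is that the primary rate itself is per woman randomised. The full analysis set includes all randomised women, but the rate is per transfer, so women without a transfer are outside it whatever section 7 says.

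**What to change.** - In Protocol sections 7 and 10.13, state that investigator withdrawal, non-compliance, stopped imaging, or closure of a site or the trial ends trial procedures but not outcome collection.
- State that hCG and scan results to weeks 10-12 are taken from clinic records for every randomised woman who has not withdrawn consent to the use of her data, unless the reason for closure itself prevents this.
- On the Trial Exit eCRF, record discontinuation and unknown outcome as separate fields.

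The cost is a protocol amendment, one eCRF field and some data queries, with no added visits. Where current consent does not cover outcomes taken from records, sections 9.2 and 10.6 imply ethics review and possibly re-consent. Across 16 centres in 7 countries that is the main burden.

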7.1 Baseline Data Collection

Before controlled ovarian stimulation (COS), potential subjects in the trial will undergo pre-ICSI/IVF preparations per the standard protocol currently in force at each site. Collection of trial-related information may take place only after the potential subject and her partner have given voluntary, documented, informed consents (ICFs).

The following information is recorded in the **Screening and Baseline eCRF**:

- · Date of Informed Consents to be signed by potential subjects and their partners;
- · Demographics, pregnancy history, cause of infertility, hormone levels (FSH, LH,

Protocol Version: 3.0 / Jan 31, 2018 25 / 49

trial

E2 and AMH) and antral follicle count (AFC) of the potential subject, as well as the date of data collection.

7.2 Data Collection on Day of Ovulation Triggering

The following data on COS and ovulation triggering is recorded in the COS and Ovulation Triggering eCRF:

- Downregulation and COS regimen, total dose of gonadotropin, type of gonadotropin, the date of the first dose of gonadotropin and the duration of COS;
- The date, time and method of ovulation triggering, and the pre-trigger hormonal and ultra-sonographic data.

7.3 Data Collection on Day 0-3 of Embryo Culture

Oocyte retrieval and ICSI/IVF will follow the local protocols/practice in place at each trial site. All oocytes/zygotes are cultured in routine culture dishes in conventional incubators for both treatment groups until fertilization check on Day 1 of embryo culture. Immediately after confirming the number of 2PN zygotes, the last step of subject screening is accomplished and randomization is conducted.

The following information is captured in the **OPU** (Oocyte pick-up) and **Insemination eCRF**:

- Date and time of oocyte retrieval, the number of oocytes retrieved and the maturation status: GV, MI, MII, and degenerated;
- Date, time and method(s) of insemination: (i) ICSI (ii) IVF (iii) both;
- Date and time of fertilization check and the number of 2PN zygotes.
- Randomization and allocation of subjects.

After randomization and allocation, the 2PN zygotes are transferred to GERI dishes with pre-equilibrated culture media and are relocated to either GERI+ incubators or conventional incubators. The embryo culture, assessment and transfer are described in detail in Section 6.8 Description to Treatment.

The following data is collected in the Embryo Culture, Assessment and Transfer eCRF:

• Embryo culture conditions (including humidification, gas phase, brand of oil and

Protocol Version: 3.0 / Jan 31, 2018 26 / 49

trial

media);

• Date and time of embryo assessment;

- Status and fate of each individual embryo;
- Date and time of embryo transfer;
- The number of embryos(s) transferred;
- The procedure of embryo transfer: with ultrasound guidance or not, and difficulty.

7.4 Data Collection on Day of hCG Test

A standard urine or blood serum hCG test is performed 12-18 days after embryo transfer, following the routine practices at the trial site. The following information is recorded in the LPS (Luteal Phase Support) and Clinical Outcome eCRF:

- · Strategy of LPS;
- · Date of the hCG test;
- · Method of hCG test and the result;
- Quantitative β -hCG, as applicable.

If the result of the hCG test is negative, the subject will have completed the trial and be exited at that time (complete **Trial Exit eCRF**).

7.5 Data Collection for Clinical Pregnancy Ultrasound Test

The ultrasound test to verify clinical pregnancy is carried out between gestational weeks 6 and 8. The following information is recorded in the LPS and Clinical Outcome eCRF:

- Date of the last ultrasound test for clinical pregnancy;
- Result
 - Number of intrauterine gestational sacs
 - Number of fetal heartbeats
 - Ectopic pregnancy (Yes or No)
 - Biochemical pregnancy (Yes or No)
 - Other

If the result of the ultrasound test is negative, that is, if no fetal heartbeat is detected, then the subject will have completed the trial and be exited at that time (complete **Trial Exit eCRF**).

Protocol Version: 3.0 / Jan 31, 2018 27 / 49

trial

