6.6 Method of Blinding

- Blinding: The trial is blinded to the subjects. The trial is not blinded to the embryologists handling the embryos or the clinicians/nurses conducting embryo transfer and pregnancy tests/scans.
- Emergency Un-blinding: in case of a medical emergency, the subject will be informed by her trial doctor or embryologist which incubator and embryo grading method are used for her embryos.

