6.10 Definition of Completion of the Study

Completion of the study is achieved when all subjects finish the test for ongoing pregnancy.

The subject may complete and exit from this trial at the following time points:

- Test for hCG 12-18 days post embryo transfer: a subject will exit from the trial if the blood or urinary test result for hCG is negative. Otherwise subject waits until the test for clinical pregnancy.
- Test for clinical pregnancy at gestational weeks 6-8: a subject will exit from the trial if the ultrasound test result for clinical pregnancy is negative. Otherwise the subject waits until the test for ongoing pregnancy.
- Test for ongoing pregnancy at gestational weeks 10-12: a subject will finish the

Protocol Version: 3.0 / Jan 31, 2018 24 / 49

trial

trial at this time point, regardless of whether the ultrasound result for ongoing pregnancy is positive or negative.

 Miscarriage: a subject will exit from the trial upon spontaneous or therapeutic miscarriage.

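### Section 7.5 exits a woman once a scan shows no heartbeat, although the primary endpoint is a heartbeat anywhere in weeks 6-8; the deciding scan is undefined and the staff who scan know the allocation

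*Protocol*

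**What the plan says.** Protocol 5.2.1 defines the primary endpoint as at least one fetus with a heartbeat, documented in gestational weeks 6 to 8. Protocol 7.5 places the scan in that window without a target day.

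Two exit rules follow:

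- Protocol 7.5: "if no fetal heartbeat is detected, then the subject will have completed the trial and be exited at that time".
- Protocol 6.10: "a subject will exit from the trial if the ultrasound test result for clinical pregnancy is negative".

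Among the items that 7.5 collects is the "Date of the last ultrasound test for clinical pregnancy".

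The weeks 10-12 scan in Protocol 7.6 is only for women already confirmed pregnant at weeks 6-8. SAP 14.1 counts as a primary success only an intrauterine pregnancy with at least one sac with a heartbeat, and the denominator is every woman with an attempted transfer. SAP 14.1 defines clinical pregnancy more widely: intrauterine pregnancy with or without a heartbeat, plus ectopic pregnancy.

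On masking, Protocol 6.6 states that the trial is "not blinded to the embryologists handling the embryos or the clinicians/nurses conducting embryo transfer and pregnancy tests/scans"; Protocol 6.2 says the same. Neither document provides a rule on repeat scans, a blinded reading or an adjudication.

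**The concern.** The endpoint stays open until the end of week 8, but the exit rule can close it at any scan in the window. If a woman has a sac without a heartbeat early in week 6, is exited, and has a heartbeat later in the window, she meets 5.2.1 but is recorded as a failure. Within an arm the error goes one way only, from success to failure.

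The wording also leaves room for different handling. One clinician may exit the woman, while another may scan again and enter the later result. Both can point to 7.5. Those performing the scan know the allocation, so the choice could differ by arm. At stake are the primary rate, the ongoing pregnancy rate and, through its denominator, the miscarriage rate.

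**Working it through.** **Step 1. Follow one woman through the text.** She has an intrauterine sac without a heartbeat at a scan early in week 6.

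| Provision | Consequence |
|---|---|
| Protocol 5.2.1 | Still able to meet the endpoint until the end of week 8 |
| Protocol 7.5, exit rule | Exited at that scan |
| Protocol 7.5, data item | A later scan would be the one recorded |
| Protocol 6.10 with the SAP 14.1 definition | Clinical pregnancy is positive, so not exited |
| Protocol 7.6 | If exited, not scanned at weeks 10-12, so no later correction |
| SAP 14.1 and 14.2.6 | Stays in the denominator; failure for the primary endpoint and for ongoing pregnancy |
| SAP 14.2.9 | In the miscarriage denominator, but exited before any loss is observed |

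These provisions do not give one answer.

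**Step 2. Reproduce the planned sample size.** Inputs from Protocol 8.1: "Based on an expected clinical pregnancy rate of 30" per cent in the control group; "a 25% relative increase of clinical pregnancy rate in the experimental group", so 30% x 1.25 = 37.5%; "a two-sided test with an alpha level of 0.05"; and "needs 623 subjects per group to reach a power of 80" per cent.

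Formula (pooled variance, no continuity correction): n = [1.960 x sqrt(2 x pbar x (1 - pbar)) + 0.842 x sqrt(p1(1 - p1) + p2(1 - p2))]^2 / (p2 - p1)^2.

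With pbar = 0.3375, n = [1.960 x sqrt(0.4472) + 0.842 x sqrt(0.4444)]^2 / 0.075^2, which rounds up to 623. Then 623 / 0.90 = 692.2, so 693 per group and 1,386 in total. The plan's figures reproduce, with power 80.0% at 623 per group.

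**Step 3. Illustrate missed heartbeats.** Let f be the share of true heartbeat pregnancies recorded as negative. The documents give no value, so every f is an assumption. The recorded rate is p x (1 - f). Power is Phi[(d - 1.960 x SE0) / SE1], where d is the difference in recorded rates, SE0 = sqrt(2 x pbar x (1 - pbar) / 623) and SE1 = sqrt((p1(1 - p1) + p2(1 - p2)) / 623).

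Same f in both arms:

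| f | Recorded rates | Power at 623 | n per group for 80% |
|---|---|---|---|
| 1% | 29.7% vs 37.1% | 79.4% | 633 |
| 2% | 29.4% vs 36.8% | 78.8% | 643 |
| 3% | 29.1% vs 36.4% | 78.2% | 652 |
| 5% | 28.5% vs 35.6% | 76.9% | 673 |
| 10% | 27.0% vs 33.8% | 73.6% | 728 |

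f in the control arm only, true rate 30% in both arms:

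| f | False difference | Two-sided rejection rate at nominal 5% |
|---|---|---|
| 2% | 30% x 0.02 = 0.6 points | 5.6% |
| 5% | 30% x 0.05 = 1.5 points | 9.0% |
| 10% | 30% x 0.10 = 3.0 points | 21.6% |

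Under the planned 30% vs 37.5%, f = 5% in the control arm only moves power to 92.3%; in the GERI+ arm only, to 56.1%.

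These figures use a simple two-proportion test in place of the stratified test in Protocol 8.4.2. SAP 7 plans no between-group comparison or confidence interval. Under the SAP the effect would therefore be bias in the descriptive rates.

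**The case against.** The strongest reply is that the plan, read as a whole, already lets the last scan decide. The endpoint covers the whole window, 7.5 refers to the scan without numbering it, and the eCRF asks for the last one. This stands as far as it goes. A reader might infer that the first scan always ends follow-up, but the text does not say so, and a repeat scan is compatible with it. It does not settle when a negative scan is final, and the exit sentence carries no such qualification.

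Within the protocol alone, 6.10 can also be read as using clinical pregnancy in the sense of 5.2.1 and so agreeing with 7.5. The conflict arises once the SAP definition is applied. Both documents govern the same data, so it needs resolving.

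A reader might also infer that unblinded clinicians choose the scan date and any repeat scan. No section assigns that choice; it is inferred from silence. Nor does anything suggest that handling would differ by arm, or in which direction. Block randomization stratified by site balances fixed site habits, which leaves arm-dependent handling within a site as the risk.

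Finally, part of the problem is already visible. SAP 14.1 tabulates by arm the intrauterine pregnancies with and without heartbeat, and separately those with heartbeat. The difference bounds the under-count among women with a visible sac. SAP 14.1 does not summarise when the deciding scan took place.

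**Conclusion.** The rule should be corrected. Section 7.5, followed literally, can record as a failure a woman who meets 5.2.1 later in the window, and nothing downstream corrects this. The exit rules and the SAP definition disagree on a sac without a heartbeat, and unblinded staff have to resolve it case by case.

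The size is unknown. If misses are equal across arms and at most about 3%, the power loss stays under 2 points. Arm-dependent handling would bias the reported rates, and would raise the error rate of the protocol's test if that test were run. Both statements rest on assumed miss rates.

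A larger figure is tempting. Suppose 40% of women destined to have a heartbeat are scanned very early and 20% of those show none yet. Then 30% x 0.40 x 0.20 = 2.4 points are lost, about a third of the planned 7.5. If all of that fell in one arm, it could look like a device effect. The documents support neither share, nor the assumption that the loss falls in one arm only.

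**What to change.** Reconcile Protocol 5.2.1, 6.10 and 7.5 with SAP 14.1 as follows:

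- The primary endpoint is classified on the last scan performed within gestational weeks 6-8.
- A woman with an intrauterine sac but no heartbeat stays in data collection until the window closes or a loss is documented. The result of any further routine-care scan in the window is entered.
- SAP 14.1 reports by arm the timing of the deciding scan and the number of women with a sac but no heartbeat.

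The rule is the same in both arms. It governs classification and data capture only, and prescribes no additional scan or clinical schedule. It therefore does not remove discretion over repeat scans; the by-arm report is there to show whether that discretion was used differently.

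Optionally, where the person scanning is neither the investigator nor an embryologist, allocation can be left off the scan request. Masking all clinical staff is a different matter. Investigators sign the eCRFs (Protocol 10.1), which hold the allocation (7.3), and they report device deficiencies (7.7.4). Emergency unblinding relies on the trial doctor or embryologist informing the subject (6.6). Blanket masking would collide with these duties.

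The cost is protocol and SAP wording, a small eCRF change and a slightly later exit for a few women.
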